## Subject Information

Target accrual: 15

Adult patients who are newly diagnosed with severe OSA and severe obesity (BMI>35) will be recruited from the Mayo Clinic Center for Sleep Medicine. A Research Study Coordinator will contact qualified patients prior to their follow-up appointment in the Sleep Center. This appointment typically takes place 2 or 3 months after the initial consultation with a sleep provider. This window will give the patient time to adjust to using their new sleep apnea machine. The study team will use Epic's Slicer Dicer feature to search the appointment return type and add the required BMI and age requirement. A member of the study team will contact via telephone eligible patients using an approved phone script. If interested, the patient will have the option of receiving the consent form electronically through Ptrax or a paper copy through the US Mail. A member of the study team is available if the patient would like to meet in person during their follow up visit with their provider. Patients may also be referred at the time of their return visit.

### Inclusion Criteria:

- 18 years of age or older
- Diagnosis of OSA
- BMI > or = to 35

### Exclusion Criteria:

- Patients with an inability to provide good data or follow commands (patients who are disoriented, have a severe neurologic or psychiatric condition).

## Review of medical records, images, specimens

The study involves data that exist at the time of IRB submission **and** data that will be generated after IRB submission. Include this activity in the Methods section.

To determine eligibility and obtain contact information, a study team member may review the participant's medical record.

## Qualitative Data Analysis

**Power Statement:** This is a feasibility study, no sample size is required.

## Data Analysis Plan:

A qualitative analysis, in the way of likert-scale questions, will be completed when the participant has completed the intervention. The qualitative approach will provide a framework for which detailed information about the participants experience is collected and eventually analyzed.

## Appendix 1:

### Withings Sleep Mat

#### Device

- **Outer material** Premium fabric
- **Dimensions and weight**
  - Length: 637mm (25")
  - Width: 190mm (7.5")
  - Thickness: 5mm (0.2")
  - Weight: 350 g (1.13 oz)
- **Sensors**
  - Pneumatic sensor: measures respiratory rate, heart beats via ballistocardiography and body movements across the mattress.
  - Sound sensor: identifies audio signals specific to snoring & cessation of breathing episodes.
- **Data storage & sync**
  - Free and unlimited online data storage with a Withings account.
  - Local storage of data between syncs.
- **Power supply**
  - Power supply 5V 1A
  - USB power adapter included

### Withings Smart Scale

#### Device

- **Four weight sensors**
  - Weighing range: 5 -> 180kg (9 -> 396lb)
  - 100g (0.2lb) graduation
  - Units: kg, lb, st lb
- **Patented body position detector**
  - Highly-accurate weighing via Position Control™ technology
- **Scale**
  - Large, high-strength tempered glass platform
  - Paint-free satin white casing
  - Ultra slim design
  - Dimensions: 12.8 x 12.8 x 0.9 in. / 327x327x23mm
- **Display**
  - Large, easy-on-the-eye graphical display (2.4" x1.6"), 128x64 pixels
  - High-contrast lighting
- **Storage and memory**
  - Free and unlimited online storage of weight readings
  - Stores up to 16 readings if scale cannot sync wirelessly
- **Power supply**
  - 4x 1.5V Alkaline cells (AAA)
  - Average battery lifetime of 18 months

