Preliminary evidence shows that an effective digital health intervention that utilizes remote monitoring and health coaching to address obesity may be as effective as an in-person program, in addition to having benefits in accessibility and scalability. Recent preliminary research also shows that this type of intervention is feasible, acceptable, and effective for older adults living in rural areas to address obesity. This is particularly important as there has been limited study of older adults participation in digital health interventions.

**Scientific Premise :** Severe OSA associated with obesity and other comorbidities is highly influenced by behavior. Early evidence suggests that health coaching is effective at supporting patients with behavior changes and chronic disease management. Health coaching associated with remote monitoring has been tested and offers promise to address behavior, including PAP use, physical activity, and mindful eating. Based on our previous NIH funded work in other chronic conditions, we hypothesize that a remote monitoring system with health coaching for severe OSA with obesity and comorbidity is feasible and may improve quality of life. Additionally, it may create conditions for behavior change resulting in increased adherence to PAP use as well as addressing obesity and other comorbid conditions. If effective these findings are extremely important to

addressing a critical health problem through a solution that is relatively inexpensive, scalable, billable, and accessible.

We propose to develop a home-based system for obese patients with OSA. The proposed system will provide patients with remote guidance, personalized reports, and monitoring integrated with health coaching. Health coaches will also receive individualized patient information, formatted in accessible and usable way.

Monitoring will include key indicators: PAP use, sleep quality, physical activity, weight and symptom days (self-reported well-being, fatigue, sleepiness, and daily activity). The system is compliant to bill for remote patient monitoring through existing Medicare and private insurance billing codes.

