## Study Design and Methods

**Methods:** *Describe in lay terms, completely detailing the research activities that will be conducted by Mayo Clinic staff under this protocol.*

The proposed system (see Figure 1) will use technology to facilitate remote health coaching for people with severe comorbid OSA with the goal of encouraging behavior change. The system will be built upon the existing home-based pulmonary rehabilitation (PR) system that was jointly developed by Mayo and MHS. The PR system was well-received and has proven effective, reliable, and easy to use. The overall architecture will be reused for the OSA coaching system, but a new set of sensors, cloud services, and data reporting capabilities will need to be integrated and developed.

The system will be designed so that a newly-diagnosed patient can immediately benefit from health coaching, including equipment setup, goal setting, and trend monitoring in all pertinent aspects of care: PAP management, sleep scheduling, sleep duration, diet, exercise, medications and more. When they register for the program, patients will be provided with a set of pre-configured sensors and a dedicated Android tablet. The tablet will exclusively run a custom-built Android application that graphs patient progress, asks periodic self-report questions, sends secure text messages between the health coach and patient, displays timely reminders, and plays helpful videos to assist with sensor use. The tablet and sensors upload the patient's activities, physiological data, and answers to the daily self-report questions to a secure website. This website also allows health coaches to view patient data via overview, weekly, daily, and trend reports. Health coaches call patients regularly to celebrate progress, assist with any issues, and set new goals.

**Figure 1.** A diagram of the proposed health coaching system.

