In the past, MHS and Mayo jointly developed an in-home PR system that was well-received and is being widely deployed. Patients receive an Android tablet running an app that plays exercise videos, graphs patient progress, asks periodic self-report questions, sends text messages between the health coach and patient, displays timely reminders, and shows instructional videos to assist with sensor use. The app runs in “kiosk” mode, ensuring that the patient cannot close the app, accidentally misconfigure the tablet, or use the tablet for other purposes (e.g., web browsing, watching movies). Each tablet has a unique API key that allows it to sync the patient’s activities, physiological data, and daily self-report answers to a secure website. Health coaches can login to this website to review the data for each of their patients.

MHS engineers will provision a web server and database for the OSA coaching system. The web server will be an AWS EC2 t2.micro instance running Ubuntu Linux 18.04 with an .NET Core 3.1 application (or newer). The database will be an AWS RDS db.t2.micro instance running MariaDB 10.3.23 (or newer).

Software development best practices will be used throughout development. All source code will be versioned using Git and backed up GitHub.com.

Patients will be provided with a system (Android tablet linked to a Withings Body Smart scale, Withings Sleep Tracking Mat, and a Withings Move Activity and Sleep Watch, see Appendix 1 for Withings device information) to take home and instructions to use it for two weeks along with their newly prescribed PAP machine. Patients will be asked to weigh themselves at least once a week, to use the PAP machine and sleep mat daily, and to monitor their steps. Patients will also be asked to complete self-report questions at least 6 of the seven days and to complete a health coaching call twice per week. The activity monitor watch is to be worn

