at all times. The participant tablet home screen display will have a simple To-Do list. To initiate an activity, the user selects the corresponding activity from the “To-Do” column. When the participant finishes the selected activity, it appears in the “Done” column. The application provides instructions before and between each activity. Participants will also be able to see limited reports of their activity as will the health coach. In phase II, this reporting capability will be flushed out. The health coaches are an established part of [name] laboratory and have been trained to support participants in the behavior change process.

The 5 self-reported questions are:

Tap the faces that best answer the following questions.					
How do you feel today?					
	POOR	FAIR	GOOD	VERY GOOD	EXCELLENT
How is your level of energy?					
	POOR	FAIR	GOOD	VERY GOOD	EXCELLENT
How was your sleep last night?					
	POOR	FAIR	GOOD	VERY GOOD	EXCELLENT
How was your CPAP experience last night? Leave blank if not used.					
	POOR	FAIR	GOOD	VERY GOOD	EXCELLENT
How was your awareness of what you ate yesterday?					
	POOR	FAIR	GOOD	VERY GOOD	EXCELLENT
CANCEL					

Following the 2 week testing period, participants will be interviewed by the Research Coordinator to provide qualitative feedback on the acceptability and usability of the system, including what they liked and did not like about the app interface, the concept of home-based system, and the health coaching. Participants will be asked to describe any struggles with using the system or past efforts in behavior change. Participants will also complete a brief socio-demographic survey. Additionally, the system securely collects and stores the following patient data: timestamped interactions with the Android app, answers to the daily questionnaire, physiological and activity data collected by the scale, sleep mat and activity monitor. All data will be reviewed and visualized to understand patient usage, identify potential barriers, and to plan further developments to the system.

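### Does the 180 kg limit of the supplied scale call for a weight rule in a study with a BMI floor and no ceiling?

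*Protocol*

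**What the plan says.** Under Study Design and Methods, each participant receives one kit: "Patients will be provided with a system (Android tablet linked to a Withings Body Smart scale", with a sleep mat and an activity watch. For specifications the text says "see Appendix 1 for Withings device information". The request that follows is general: "Patients will be asked to weigh themselves at least once a week", over a two-week test.

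Appendix 1, under the smart scale, states "Weighing range: 5 -> 180kg (9 -> 396lb".

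The Inclusion Criteria give a lower BMI bound of 35. Subject Information repeats a floor and describes a record search on appointment type, BMI and age. Neither gives a ceiling. The single Exclusion Criterion concerns people who cannot give good data or follow commands, and its bracket explains this by mental, neurologic or psychiatric state, not body size.

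On the role of weight, the Scientific Premise says "Monitoring will include key indicators: PAP use, sleep quality, physical activity, weight and symptom days". On supervision, the Methods say "Health coaches call patients regularly to celebrate progress, assist with any issues, and set new goals", and participants are asked "to complete a health coaching call twice per week". The system also stores "timestamped interactions with the Android app" alongside the scale data.

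**The concern.** The study recruits people with severe obesity and gives them a scale with an upper limit. Eligibility has a floor only, so the protocol can admit someone the scale is not specified to weigh and then ask that person to use it every week. Nothing prompts the team to compare weight with the scale's range before the kit goes out.

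Weight is a named monitoring indicator, and the scale data enter the review of how participants used the system. If the scale gave no valid reading for such a person, a missing weight could be taken for failure to step on the scale when the cause was the equipment. In a feasibility study that distinction matters, because usage and barriers are what it reports.

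**Working it through.** **Inputs from the protocol.** Scale limit 180 kg, printed also as 396 lb (Appendix 1). BMI floor 35 (Inclusion Criteria). Target accrual 15 (Subject Information). Two weeks, at least one weighing a week (Study Design and Methods). The protocol gives no distribution of body weight.

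**1. The stated limit.** 180 × 2.20462 = 396.8 lb, which agrees with the printed 396 lb when truncated. The lower limit does not convert cleanly (5 × 2.20462 = 11.0 lb, printed as 9 lb), but that is irrelevant to adults with a BMI of at least 35.

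**2. What 180 kg means as a BMI.** BMI = 180 / height², and weight at the floor = 35 × height².

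| Height (m) | BMI at 180 kg | Weight at BMI 35 (kg) | Margin to 180 kg (kg) |
|---|---|---|---|
| 1.65 | 66.1 | 95.3 | 84.7 |
| 1.75 | 58.8 | 107.2 | 72.8 |
| 1.85 | 52.6 | 119.8 | 60.2 |
| 1.95 | 47.3 | 133.1 | 46.9 |

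A person exactly at the floor would reach 180 kg only at a height of √(180/35) = 2.27 m. The criteria do admit people above 180 kg, but only well above the floor.

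**3. How often it might arise.** Let p be the assumed share of eligible patients above 180 kg. With 15 participants, the expected number is 15p, P(at least one) = 1 − (1 − p)¹⁵, and P(zero or one) = (1 − p)¹⁵ + 15p(1 − p)¹⁴.

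| p (assumed) | Expected number | P(at least one) | P(zero or one) |
|---|---|---|---|
| 0.1% | 0.015 | 1.5% | >99.9% |
| 0.5% | 0.075 | 7.2% | 99.7% |
| 1% | 0.15 | 14.0% | 99.0% |
| 5% | 0.75 | 53.7% | 82.9% |

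**4. Share of the data.** The minimum number of home weighings is 15 × 2 = 30. One affected participant accounts for 2 of 30, or 6.7%.

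**5. What those readings feed.** The Data Analysis Plan describes Likert-type questions and the participants' experience. The Methods add that stored data will be reviewed and visualised to understand usage and barriers. The protocol sets no weight endpoint, no weighing-adherence rate and no threshold that a missing weight could move.

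**6. What would reveal the case.** Coaches can see each participant's data and help with problems. At two calls a week for two weeks there are four calls per participant. App interactions are timestamped, and the closing interview asks about struggles with the system. A participant whose scale does not work for them has several chances to say so.

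**The case for a change.** The strongest case for a change is that eligibility and the issued equipment are protocol matters, so a statistical analysis plan cannot be expected to fill this gap. The exclusion for people unable to give good data does not fill it either, since its bracket limits it to mental state. The coach calls and the interview act only once the kit is in the home. None of them screens beforehand, and none fixes how a missing weight is labelled. A check against the recorded weight would cost little, and a scale that does not cover the whole eligible population is itself worth knowing before later development.

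The factual part of this stands: the text is silent on weights above 180 kg. The consequence does not follow. The protocol does not say what the scale does above its range, so neither a lost reading nor a wrong one can be asserted. The protocol has no class of use or non-use into which a missing weight would be wrongly put; an analyst would look at the coach's record and the interview before naming a cause. A fixed rule could make matters worse. Attributing every absent weight in a heavy participant to the device would presume the cause and could hide true non-use. Supplying a different scale would mean that person tests a different system. The cost is also not quite nil: BMI is applied as a search filter, and record review is described for eligibility and contact details, so matching equipment to weight would be an additional purpose. Finally, finding that a component does not suit some participants is a legitimate result of this study, and the route for reporting it already exists.

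**Conclusion.** No change to the plan is needed. The protocol is silent on an uncommon case; it does not contradict itself or state a wrong figure. The BMI floor and the scale's range are compatible for everyone up to 180 kg. Above that, the likely number affected is zero or one of 15, with an assumed share of 0.1% to 5% behind that reading. At the upper end of that range, at least one case is about as likely as not (53.7%). Even then, one person's two minimum weighings are 6.7% of the minimum total, and the protocol describes no analysis of weight that they could distort.

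The conclusion rests on three things: the assumed range of shares, the absence of any weight endpoint in the protocol, and coach contact and the closing interview taking place as described. Staff who notice a heavy participant when preparing a kit can deal with it as a practical matter, and the usage review can record the scale's limit as a barrier without new wording. If weight change became a formal outcome in a later phase, the match between the scale's range and the eligible population would deserve attention then.

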## Withings Move Activity and Sleep Watch

### Device

- **Materials**  
Withings Move comes with a plastic case and a stainless steel bottom case with a silicone wristband.
- **Single battery charge lasts**  
Up to 18 months (CR2430)
- **Storage & memory**  
Free and unlimited online data storage with a Withings account  
5 days of local storage of data between syncs
- **Usage instruction**  
Workout mode: Launch workout mode with a long press on the watch button. It will activate a timer directly on the watch, and it will activate the connected GPS feature.

### Metrics tracked

- **Metrics**  
Walking and running: Steps, distance, calories  
Swimming: Session duration, calories  
Sleep: Deep and light sleep phases, sleep interruptions  
Automatic detection of activities, no need for user's action  
Connected GPS: distance, pace & elevation
